#### **7.1.7.2 Safety Analysis Populations**

The All Subjects as Treated (ASaT) population will be used for the analysis of safety data in this trial. The ASaT population consists of all subjects who received at least one dose of trial treatment. At least one laboratory or vital sign measurement obtained subsequent to at least one dose of trial treatment is required for inclusion in the analysis of each specific parameter. To assess change from baseline, a baseline measurement is also required.

Details on the approach to handling missing data for safety analyses are provided in Section 7.1.8.1 Statistical Methods.

For safety analysis related to AE rate, the AE evaluable population will be used. The AE evaluable population consists of all AE evaluable subjects. In order to be considered evaluable, the subject must complete the first cycle of therapy or discontinue from the trial due to a drug-related adverse event. Subjects who discontinue prematurely due to a non-drug-related cause are not included in the AE evaluable population.

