#### **3.2.3.2 Safety Endpoints**

The primary safety objective of this trial is to characterize the safety and tolerability of pembrolizumab (MK-3475), lenalidomide and dexamethasone in subjects with high-risk MM post-ASCT. The primary safety analysis will be based on subjects who experienced toxicities as defined by CTCAE criteria version 4.03. Safety will be assessed by quantifying

the toxicities and grades experienced by subjects who have received pembrolizumab (MK-3475), lenalidomide and dexamethasone, including serious adverse events (SAEs).

Safety will be assessed by reported adverse experiences using CTCAE, Version 4.03. The attribution to drug, time-of-onset, duration of the event, its resolution, and any concomitant medications administered will be recorded. AEs will be analyzed including but not limited to all AEs, SAEs, fatal AEs, and laboratory changes.

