### 7.1.2 Safety Analysis

The All-Subjects-as-Treated (ASaT) population will be employed for safety analyses. The ASaT population consists of all subjects who received at least one dose of trial treatment. Subjects who entered the study and did not take any of the study drug(s) and had this confirmed, will not be evaluated for safety.

Descriptive tables that summarize the number and percentage of subjects that experience adverse events as categorized in the NCI CTCAE Version 4 will be generated by dose level.

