### **7.1.6.2 Safety Endpoints**

The primary safety endpoints include the AEs graded using CTCAE (Version 4.03) criteria. Safety will be assessed by quantifying the toxicities and grades experienced by subjects who have received pembrolizumab (MK-3475), including serious AEs and events of clinical interest (ECIs). Immune-related AEs (irAEs), as defined in Section 6.2.3.2 will be collected. Other safety endpoints include laboratory safety assessments, vital signs and physical examinations. Safety measurements are described in Section 6.

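### AE percentages have two denominators: all treated subjects (7.1.2), or a set that drops those who leave in cycle 1 for a cause judged not drug-related (7.1.7.2)

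*Combined protocol and SAP*

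**What the plan says.** Section 7.1.2 states the safety population without exception: "The All-Subjects-as-Treated (ASaT) population will be employed for safety analyses". It defines ASaT as subjects with at least one dose and names no other set. In the same section it plans the main AE output: "Descriptive tables that summarize the number and percentage of subjects that experience adverse events as categorized in the NCI CTCAE Version 4".

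Section 7.1.7.2 begins the same way: "The All Subjects as Treated (ASaT) population will be used for the analysis of safety data in this trial". Its last paragraph then introduces a second set: "For safety analysis related to AE rate, the AE evaluable population will be used". To belong to it, "the subject must complete the first cycle of therapy or discontinue from the trial due to a drug-related adverse event". The paragraph closes with an exclusion: "Subjects who discontinue prematurely due to a non-drug-related cause are not included in the AE evaluable population".

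Section 7.1.8.2, which covers safety methods, says AEs will be summarised as counts, frequencies and grades but names no population. Section 7.0 says there will be no separate SAP.

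**The concern.** The percentage of subjects with an AE is an AE rate in ordinary usage, and the plan gives that term no other meaning. The same table is therefore assigned to two different sets.

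The choice matters because the AE-evaluable set is defined by what happens after dosing and by an open-label causality judgement in a trial with no concurrent control arm. Take two treated subjects who both stop in cycle 1, one for an AE judged drug-related and one for an intercurrent illness judged unrelated (a listed reason for discontinuation in 4.8). The first is counted. The second is removed, together with every AE that subject had. A subject who dies in cycle 1 of a cause judged unrelated is removed in the same way.

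Safety and tolerability is the first secondary objective in 2.2, and 1.1 lists safety among the primary objectives. At stake is whether the reported toxicity rates describe everyone exposed to the regimen.

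**Working it through.** **1. Does any text settle the conflict?**

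- 7.1 refers the reader to 7.1.8 for full detail. In 7.1.8.2 no population is attached to the AE counts and frequencies.
- 7.1.7.2 refers to 7.1.8.1 for missing safety data, but 7.1.8.1 is the efficacy section and does not cover safety.
- Table 13 in 7.1.8.1 shows that the plan can rank sets: for response rates, FAS is primary and ITT supportive. Nothing similar exists for ASaT and the AE-evaluable set.
- 3.2.3.2 describes safety as "the toxicities and grades experienced by subjects who have received pembrolizumab" and the other two drugs, and 7.1.6.2 uses similar words. That is the ASaT concept, but neither section mentions the AE-evaluable set, so they support ASaT without resolving the conflict.

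**2. Is membership of the second set clear?** Not fully. The inclusion sentence makes anyone who completes cycle 1 evaluable. The exclusion sentence has no cycle limit. Reading premature departure as departure before the end of cycle 1 is the most natural way to make the two agree, but it is not stated.

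**3. How far can a percentage move?** The plan gives no figure for the AE-evaluable set, so there is none to reproduce. Inputs:

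- N = 43, the total in 7.1.3. Treating all 43 as dosed is an assumption.
- x = 10 treated subjects with the AE (assumed).
- k = 1 to 3 subjects who leave in cycle 1 for a cause judged not drug-related (assumed; the documents give no rate).
- j = the number of those k who had the AE, from 0 to k.

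ASaT rate = x/N = 10/43 = 23.26%. AE-evaluable rate = (x − j)/(N − k).

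| k | All departures had the AE (j = k) | Change, points | None had it (j = 0) | Change, points |
|---|---|---|---|---|
| 1 | 9/42 = 21.43% | −1.83 | 10/42 = 23.81% | +0.55 |
| 2 | 8/41 = 19.51% | −3.74 | 10/41 = 24.39% | +1.13 |
| 3 | 7/40 = 17.50% | −5.76 | 10/40 = 25.00% | +1.74 |

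The exact (Clopper-Pearson) 95% interval for 10/43 is 11.8% to 38.6%, so every value in the table lies inside it.

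**4. Less frequent events.** With x = 5, ASaT gives 5/43 = 11.6%. With k = 3, the AE-evaluable rate is 5/40 = 12.5% if none of the three had the event, 4/40 = 10.0% if one did, and 2/40 = 5.0% if all three did. For an event seen in one patient only, for example a single cycle-1 death judged neither drug-related nor due to progression (assumed), ASaT gives 1/43 = 2.3% and the AE-evaluable table gives 0/42 = 0%.

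**The case against.** The strongest reply is that 7.1.7.2 states a general rule and then a specific one, and that an analyst looking for a denominator would go to the section on safety populations. ASaT would then cover safety data in general and the AE-evaluable set would cover AE rates. In 7.1.2 the AE-table sentence is a separate paragraph that does not repeat the population, and AE rate is undefined, so the clash depends on equating it with the percentage of subjects. This reading makes 7.1.7.2 coherent, but it does not help the plan: it makes the AE-evaluable set govern AE percentages, contrary to the only population named in 7.1.2.

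The paragraph may also be leftover dose-finding text. The plan still speaks of dose levels in 7.1.2, 7.1.6 and 7.1.8.2, and the abbreviations include dose-limiting toxicity and maximum tolerated dose. That may explain how the paragraph got there, but it remains an instruction.

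The points about consequence largely stand:

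- AEs are recorded for everyone from consent to 30 days after treatment (6.2), and SAEs are reported whether or not related (6.2.3.1).
- Reasons for discontinuation are displayed (7.1.8.3), and the DSMC reviews toxicities every 6 months (9.7).
- The stopping rules in 7.1.2 count deaths and grade 4 non-hematologic toxicity regardless of relationship and name no analysis set, so they are not shown to depend on this choice.
- Overall survival counts deaths from any cause in all enrolled subjects.
- AE summaries are descriptive, with no test.

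**Conclusion.** The concern holds. The plan gives AE percentages two incompatible denominators and no rule for choosing between them. The more specific instruction leads to the weaker set, which leaves out treated patients on the basis of a post-dose outcome and an unblinded attribution.

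The size is limited. Under the assumed counts (43 treated, 10 with the AE, one to three excluded), the shift runs from −5.8 to +1.7 percentage points, within the sampling uncertainty of the estimate. The relative effect is largest for rare events, where one excluded patient can take a reported rate from 2.3% to zero. Monitoring and expedited reporting are not affected. What remains is that two analysts following the text could publish different AE percentages from the same data. This should be corrected, but it does not threaten the efficacy conclusion.

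**What to change.** State in 7.1.7.2 and 7.1.8.2 that all AE counts and percentages use ASaT. Then either delete the AE-evaluable paragraph, or keep that set for a labelled supplementary table only, with the exclusion expressly limited to subjects who leave before completing cycle 1.

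The cost is one or two sentences in each section. No new data are needed, because AEs are already collected for all subjects.

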## 7.1.8 Statistical Methods

### 7.1.8.1 Statistical Methods for Efficacy Analysis

Kaplan-Meier estimates and corresponding 95% confidence intervals of time to event endpoints, including PFS, OS, TTP and DOR, will be provided.

For key efficacy endpoints including CR + sCR + VGPR rate + ORR, the point estimate, 90% confidence interval and p-value for testing response rate is greater than the historical control for each arm will be provided using exact binomial distribution.

Table 13 Summarizes key efficacy analyses.

Table 13 Analysis Strategies for Key Efficacy Variables

Endpoint/Variable (Description, Time Point)	Primary vs. Supportive Approach	Analysis Population	Statistical Method	Missing Data Approach
Primary				
PFS	P	ITT	Summary statistics using Kaplan- Meier method	Censored at last disease assessment date
Secondary				
ORR per IMWG criteria based on investigator assessment	P S	FAS ITT	Exact test of binomial parameter	Subjects with missing data are considered as non-responders
CR+sCR+VGPR response rate per IMWG criteria based on investigator assessment	P S	FAS ITT	Exact test of binomial parameter	Subjects with missing data are considered as non-responders
OS	P	ITT	Summary statistics using Kaplan- Meier method	Censored at the last date known to be alive
TTP	P	ITT	Summary statistics using Kaplan- Meier method	Censored at the last non- PD assessment date
DOR	P	All responders	Summary statistics using Kaplan- Meier method	Non-responders are excluded in analysis

### 7.1.8.2 Statistical Methods for Safety Analyses

Safety and tolerability will be assessed by clinical review of all relevant parameters including adverse experiences (AEs), ECOG, laboratory tests, vital signs, and ECG measurements.

Summary statistics (median and range) for time to onset of first drug-related toxicity in each dose level will be provided. Adverse experiences will be summarized as counts, frequencies and grade by NCI CTCAE version 4.03. Laboratory values will be graded by NCI CTCAE version 4.03. The percentage of subjects with laboratory abnormalities by grades will be tabulated. The change of grades during the study will be summarized by a lab shift table. In this analysis, the percentage of subjects who improve or worsen from baseline for each laboratory test will be summarized. A clinically meaningful worsening in CTCAE grade was defined as a shift from less than Grade 3 at baseline to Grade 3 or above, or a shift from Grade 0 to Grade 2. Summary statistics for baseline, on-treatment, and change from baseline values of continuous measures such as changes from baseline in ECOG, laboratory, vital signs, and ECG parameters will be provided by dose-level in table format. Immune-related AEs (irAEs) that are designated as events of special interest will be summarized separately from other AEs.

### 7.1.8.3 Summaries of Baseline Characteristics, Demographics, and Other Analyses

#### Demographic and Baseline Characteristics

Each relevant characteristic will be assessed by the use of tables/graphs. No statistical hypothesis tests will be performed on these characteristics. The number and percentage of subjects screened, the primary reasons for screening failure, and the primary reason for discontinuation will be displayed. Demographic variables (such as age) and baseline characteristics will be summarized by treatment either by descriptive statistics or categorical tables.

The reason for exclusion from the Full Analysis Set (if any) will be summarized.

#### Exploratory Analyses

Change from baseline in bone marrow aspirate/biopsy PD-L1 expression will be summarized by dosing schedules using descriptive statistics.

Comparison of change from baseline in bone marrow aspirate/biopsy PD-L1 expression between responders with longer duration of response and non-responders or responders with a short duration of response will be performed using mixed regression analysis. Longitudinal analysis of bone marrow aspirate/biopsy PD-L1 expression over time will be examined using mixed model repeated measure design with levels observed serially over time and response type (long responders vs short responders/non-response) as a fixed variable.

Longitudinal analysis will be performed on blood samples collected at time points 1) screening visit 2) Day 1 of Cycle 1, 3 ) Day 1 of Cycle 2, 3) Day 1 of Cycle 3, 4) Day 1 of Cycle 4, 5) Post completion of Cycle 4. Discrete variables such as cell counts of the absolute number of inflammatory cytokines (TNF-alpha, IL-2, IL-4, IL-6, IL-10) and activated T cells (CD8+) will be examined for changes over time using Poisson Regression Analysis based on generalized estimating equations (GEE) method obtained by utilizing PROC GENMOD SAS 9.4 with Poisson distribution, log link function and independent covariance structure. The repeated counts will be compared between long responders vs short responders/non-responders.

Longitudinal analysis of specific intestinal microbial strains identified from blood and stool samples collected at time points 1) screening visit 2) Day 1 of Cycle 1, 3 ) Day 1 of Cycle 2, 3) Day 1 of Cycle 3, 4) Day 1 of Cycle 4, 5) Post completion of Cycle 4, will be performed using GEE method described above with type of responder as grouping variable.

### **7.1.9 Multiplicity**

There is no multiplicity adjustment planned for this study.

### **7.1.10 Sample Size and Power Calculations**

Using a Simon's two-stage design, this study has 80% power at a one-sided significance level of 0.05 to discount an 'ineffective' progression-free survival (PFS) rate of 50% (p0) in favor of a PFS rate of at least 70% (p1).

A total of 15 patients will be accrued in stage one and, if successful, a further 28 patients will be accrued in stage two, bringing the total number of patients required to 43 evaluable patients. There will be a planned stopping rule in recruitment between stages 1 and 2.

### **7.1.11 Subgroup Analyses and Effect of Baseline Factors**

There is no formal subgroup analysis for this study.

### **7.1.12 Interim Analysis**

The study will stop and treatment will be rejected if there are 8 or fewer patients are progression free at 12 months. If 9 or more of the first 15 patients have not progressed at 12 months, a further 28 patients will be recruited into the second stage. The optimal design has an expected sample size of 23.5 and probability of early termination of 0.696. If the overall PFS is 70% or above at 12 months, pembrolizumab, lenalidomide and dexamethasone will be considered to have shown worthwhile efficacy. A safety analysis will also be conducted at this time and the study will be terminated if the safety stopping rules are met (See section 7.1.2).

### **7.1.13 Compliance (Medication Adherence)**

Drug accountability data for trial treatment will be collected during the study. Compliance with pembrolizumab (MK-3475), lenalidomide and dexamethasone treatment administration will be measured by subjects: 1) receiving unscheduled study agent infusions/injections; or 2)

missing an infusion/injection. Numbers and percentages of subjects and infusion/injection visits with any deviation in these measures will be reported for the ITT population.

Compliance will be defined as the percentage of the “Number of Days on Therapy” over the “Number of Days Should be on Therapy”. A day within the study will be considered an “On-Therapy” day if the subject takes study drug on a scheduled day for treatment administration without dose variation or with dose variation, including dose reduction and dose interruption, for reasons other than non-compliance. For each subject, the “Number of Days Should be on Therapy” is the total number of scheduled days for treatment administration from entry to the study to the date of discontinuation.

For each subject, percent compliance will then be calculated using the following formula:

$$\frac{\text{Number of Days on Therapy}}{\text{Number of Days Should be on Therapy}} \times 100.$$

Summary statistics will be provided on percent compliance by treatment group for the ASaT population.

## **8.0 LABELING, PACKAGING, STORAGE AND RETURN OF CLINICAL SUPPLIES**

### **8.1 Investigational Product**

The investigator shall take responsibility for and shall take all steps to maintain appropriate records and ensure appropriate supply, storage, handling, distribution and usage of investigational product in accordance with the protocol and any applicable laws and regulations.

Table 14 Product Descriptions

Product Name & Potency	Dosage Form
Pembrolizumab 50 mg	Lyophilized Powder for Injection
Pembrolizumab 100 mg/ 4mL	Solution for Injection

## **8.2 Packaging and Labeling Information**

Clinical supplies will be affixed with a clinical label in accordance with regulatory requirements.

## **8.3 Clinical Supplies Disclosure**

This trial is open-label; therefore, the subject, the trial site personnel, the Sponsor and/or designee are not blinded to treatment. Drug identity (name, strength) is included in the label text; random code/disclosure envelopes or lists are not provided.

## **8.4 Storage and Handling Requirements**

Clinical supplies must be stored in a secure, limited-access location under the storage conditions specified on the label.

Receipt and dispensing of trial medication must be recorded by an authorized person at the trial site.

Clinical supplies may not be used for any purpose other than that stated in the protocol.

## **8.5 Returns and Reconciliation**

The investigator is responsible for keeping accurate records of the clinical supplies received from Merck or designee, the amount dispensed to and returned by the subjects and the amount remaining at the conclusion of the trial. Upon completion or termination of the study, all unused and/or partially used investigational product will be destroyed at the site per institutional policy. It is the Investigator's responsibility to arrange for disposal of all empty containers, provided that procedures for proper disposal have been established according to applicable federal, state, local and institutional guidelines and procedures, and provided that appropriate records of disposal are kept.

# **9.0 ADMINISTRATIVE AND REGULATORY DETAILS**

## **9.1 Confidentiality**

### **9.1.1 Confidentiality of Data**

All information regarding this trial will be maintained in confidence, and such information will be divulged to the institutional review board, ethics review committee (IRB/ERC) or similar or expert committee; affiliated institution and employees, only under an appropriate understanding of confidentiality with such board or committee, affiliated institution and employees. Data generated by this trial will be considered confidential by the investigator,

except to the extent that it is included in a publication as provided in the Publications section of this protocol.

### **9.1.2 Confidentiality of Subject Records**

By signing this protocol, the investigator agrees that the Sponsor (or Sponsor representative), IRB/ERC, or regulatory authority representatives may consult and/or copy trial documents in order to verify worksheet/case report form data. By signing the consent form, the subject agrees to this process. If trial documents will be photocopied during the process of verifying worksheet/case report form information, the subject will be identified by unique code only; full names/initials will be masked prior to transmission to the Sponsor.

By signing this protocol, the investigator agrees to treat all subject data used and disclosed in connection with this trial in accordance with all applicable privacy laws, rules and regulations.

## **9.2 Compliance with Financial Disclosure Requirements**

Financial Disclosure requirements are outlined in the US Food and Drug Administration Regulations, Financial Disclosure by Clinical Investigators (21 CFR Part 54). It is the Sponsor's responsibility to determine, based on these regulations, whether a request for Financial Disclosure information is required. It is the investigator/subinvestigator(s) responsibility to comply with any such request.

The investigator/subinvestigator(s) agree, if requested by the Sponsor in accordance with 21 CFR Part 54, to provide his/her financial interests in and/or arrangements with the Sponsor to allow for the submission of complete and accurate certification and disclosure statements. The investigator/subinvestigator(s) further agree to provide this information on a Certification/Disclosure Form, commonly known as a financial disclosure form, provided by the Sponsor or through a secure password-protected electronic portal provided by the Sponsor. The investigator/subinvestigator(s) also consent to the transmission of this information to the Sponsor in the United States for these purposes. This may involve the transmission of information to countries that do not have laws protecting personal data.

## **9.3 Compliance with Law, Audit and Debarment**

By signing this protocol, the investigator agrees to conduct the trial in an efficient and diligent manner and in conformance with this protocol; generally accepted standards of Good Clinical Practice (e.g., International Conference on Harmonization of Technical Requirements for Registration of Pharmaceuticals for Human Use Good Clinical Practice: Consolidated Guideline and other generally accepted standards of good clinical practice); and all applicable federal, state and local laws, rules and regulations relating to the conduct of the clinical trial.

The investigator also agrees to allow monitoring, audits, IRB/ERC review and regulatory authority inspection of trial-related documents and procedures and provide for direct access to all trial-related source data and documents.

The investigator agrees not to seek reimbursement from subjects, their insurance providers or from government programs for procedures included as part of the trial reimbursed to the investigator by the Sponsor.

The investigator shall prepare and maintain complete and accurate trial documentation in compliance with Good Clinical Practice standards and applicable federal, state and local laws, rules and regulations; and, for each subject participating in the trial, provide all data, and, upon completion or termination of the clinical trial, submit any other reports to the Sponsor as required by this protocol or as otherwise required pursuant to any agreement with the Sponsor.

Trial documentation will be promptly and fully disclosed to the Sponsor by the investigator upon request and also shall be made available at the trial site upon request for inspection, copying, review and audit at reasonable times by representatives of the Sponsor or any regulatory authorities. The investigator agrees to promptly take any reasonable steps that are requested by the Sponsor as a result of an audit to cure deficiencies in the trial documentation and worksheets/case report forms.

The investigator must maintain copies of all documentation and records relating to the conduct of the trial in compliance with all applicable legal and regulatory requirements. This documentation includes, but is not limited to, the protocol, worksheets/case report forms, advertising for subject participation, adverse event reports, subject source data, correspondence with regulatory authorities and IRBs/ERCs, consent forms, investigator's curricula vitae, monitor visit logs, laboratory reference ranges, laboratory certification or quality control procedures and laboratory director curriculum vitae. By signing this protocol, the investigator agrees that documentation shall be retained until at least 2 years after the last approval of a marketing application in an ICH region or until there are no pending or contemplated marketing applications in an ICH region or until at least 2 years have elapsed since the formal discontinuation of clinical development of the investigational product. Because the clinical development and marketing application process is variable, it is anticipated that the retention period can be up to 15 years or longer after protocol database lock. The Sponsor will determine the minimum retention period and notify the investigator when documents may be destroyed. The sponsor also recognizes that documents may need to be retained for a longer period if required by local regulatory requirements. All trial documents shall be made available if required by relevant regulatory authorities. The investigator must consult with and obtain written approval by the Sponsor prior to discarding trial and/or subject files.

ICH Good Clinical Practice guidelines recommend that the investigator inform the subject's primary physician about the subject's participation in the trial if the subject has a primary physician and if the subject agrees to the primary physician being informed.

The investigator will promptly inform the Sponsor of any regulatory authority inspection conducted for this trial.

Persons debarred from conducting or working on clinical trials by any court or regulatory authority will not be allowed to conduct or work on this Sponsor's trials. The investigator will immediately disclose in writing to the Sponsor if any person who is involved in conducting the trial is debarred or if any proceeding for debarment is pending or, to the best of the investigator's knowledge, threatened.

In the event the Sponsor prematurely terminates a particular trial site, the Sponsor will promptly notify that trial site's IRB/IEC.

